5.6. Height and Weight

Height and weight will be measured at the time points specified in [Appendix B](#). For subjects who are ≤ 18 years of age, height and weight data will be used to derive WFA and SFA. Z-scores and percentiles for WFA and SFA will be determined based on CDC growth charts ([Kuczmarski et al., 2002](#)). For subjects who are > 18 years of age, age-normalized percentiles for height will be derived at Baseline, to provide insights into the potential impact of LAL Deficiency on growth.

Refer to the SOM for further detail on the measurement of height and weight.

5.7. Vital Signs

Vital signs, including pulse rate, respiratory rate, systolic and diastolic blood pressure, and body temperature (obtained by a consistent method for all measurements at a given infusion visit) will be obtained at the time points specified in [Appendix B](#). On dosing days, vital signs will be recorded pre-infusion, every 30 minutes (± 10 min) during the infusion and every 30 minutes (± 10 min) from 0 to 2 hours after the end of the infusion. Note: The end of the infusion occurs before administration of the sodium chloride flush.

Beginning at Week 24, the post-infusion period for vital sign monitoring may be shortened to 1 hour for subjects who have completed at least 22 weeks of treatment with no occurrence of moderate or severe IARs and with approval from the Sponsor. In such cases, the post-infusion monitoring period may need to be extended back to 2 hours if subjects begin experiencing moderate or severe IARs during or shortly after the infusions.

Throughout the study, additional readings may be taken at the discretion of the Investigator.

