3.1. Overview of Study Design

This open-label, multicenter study will evaluate the safety and efficacy of sebelipase alfa in a broad population of subjects with LAL Deficiency. Such subjects may have been excluded from enrollment in other studies of LAL Deficiency because of age, disease progression, previous treatment by hematopoietic stem cell or liver transplantation, less common disease manifestations, or disease characteristics that would preclude participation in a placebo-controlled study. Factors which may have rendered a subject ineligible include but are not limited to the following:

- Age at symptom onset,
- Severity of symptoms due to disease progression,
- Previous hematopoietic or liver transplantation,
- Atypical or underappreciated clinical manifestation of LAL Deficiency in the absence of elevated ALT or early onset growth failure, including, for example, mesenteric lymphadenopathy, pulmonary hypertension, or impaired growth.

The study will consist of a screening period of up to 45 days, a treatment period of up to 96 weeks, an expanded treatment period of a maximum of up to 48 weeks, and a follow-up phone call at least 4 weeks after the last dose of sebelipase alfa.

All subjects will initiate treatment with sebelipase alfa at a dose of $1 \text{ mg}\cdot\text{kg}^{-1}$ qow. A dose escalation to $3 \text{ mg}\cdot\text{kg}^{-1}$ qow may be considered for a subject who exhibits significant clinical progression and meets protocol-defined criteria for dose-escalation. A further dose increase to $3 \text{ mg}\cdot\text{kg}^{-1}$ qw may be considered for subjects exhibiting significant clinical progression. All dose escalations are contingent upon acceptable safety and tolerability of preceding infusions (see [Section 6.1](#)) and Sponsor approval.

At any time during the study, subjects who are receiving a dose of sebelipase alfa that is not well tolerated may receive a dose reduction at the Investigator's discretion. If a subject cannot tolerate the lowest possible dose of $0.35 \text{ mg}\cdot\text{kg}^{-1}$ qow, despite measures taken to manage any IARs, he/she will be discontinued from the study. The per-protocol schedule of assessments will be modified for subjects who have a dose change to allow for closer monitoring of laboratory values around the period of change.

Sebelipase alfa dosing is thoroughly discussed in [Section 6.1](#).

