5.9.4. Clinical Laboratory Collection for Dose Changes

Subjects who undergo a dose modification, as described in [Section 6.1](#), or changes in lipid-lowering therapies, as described in [Section 4.5](#), will have the following additional laboratory monitoring schedule of selected analytes:

- Prior to the first infusion of new dose/schedule or change in lipid-lowering medication: serum lipid panel, liver panel, hematology, serum chemistry, ferritin, hs-CRP;
 - For dose modifications only: at the first infusion of new dose/schedule, a predose blood sample will be collected for ADA and serial blood samples will be collected for a determination of sebelipase alfa serum concentrations according to the sampling schedule shown in [Table 2](#) (pediatric subjects) or [Table 3](#) (adult subjects).
- 4 weeks after starting new dose/schedule or change in lipid-lowering medication: serum lipid panel, liver panel;
- 8 weeks after starting new dose/schedule or change in lipid-lowering medication: serum lipid panel, liver panel;
- 12 weeks after starting new dose/schedule or change in lipid-lowering medication: serum lipid panel, liver panel, hematology, serum chemistry.

In the event that any of the above additional laboratory monitoring time points coincides with the standard laboratory assessment, the standard laboratory assessment will supersede the additional laboratory monitoring (see [Appendix B](#)).

If a subject's blood volume threshold for weight or clinical status limit collection of samples on the scheduled visit date, the Sponsor or medical monitor should be consulted for guidance with regard to a modified schedule for that visit.

Table 1 Clinical Laboratory Tests

| Laboratory Panel | Tests |
|---|---|
| Hematology | White blood cell count; red blood cell count; hemoglobin; hematocrit; mean corpuscular volume, hemoglobin, and hemoglobin concentration (MCV, MCH, MCHC); platelet count; neutrophil; lymphocytes; monocytes; eosinophils; basophils; peripheral smear for examination of cell morphology |
| Liver Function Tests | ALT, AST, alkaline phosphatase, GGT, albumin, bilirubin (direct, indirect, total) |
| Serum Lipids | LDL-C, total cholesterol non-HDL-C, triglyceride, HDL-C |
| Other Chemistries | Serum electrolytes (sodium, potassium, chloride, calcium, magnesium, phosphorus), glucose, creatinine, bicarbonate, total protein, blood urea nitrogen, hs-CRP |
| | HbA1c |

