6.1. Treatment Administered

All eligible subjects will receive repeat IV infusions of sebelipase alfa at an initial dose of $1 \text{ mg}\cdot\text{kg}^{-1}$ qow. Consecutive infusions must be at least 7 days apart. All study infusions will be administered by qualified medical personnel. Up to and including Week 24, study infusions are recommended to be administered over approximately 2 hours. After Week 24, infusions may be administered over approximately 1 hour, as tolerated by the subject (see [Section 6.5.2](#)). Prior to any infusion of sebelipase alfa, the subject will be assessed for signs and symptoms of an acute illness, including but not limited to: vomiting, fever, upper respiratory or gastrointestinal infection. If an acute illness is suspected, it is recommended that the Investigator determine whether to hold the study drug dose for that visit. In case of any questions, the Medical Monitor must be consulted.

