6.1.1. Dose Escalation Criteria

Dose escalation up to $3 \text{ mg}\cdot\text{kg}^{-1}$ qw will be considered for each individual subject based on observed safety and tolerability and disease progression. Dose escalation will occur at the discretion of the Investigator and with approval of the Sponsor. An initial dose increase to $3 \text{ mg}\cdot\text{kg}^{-1}$ qow may be considered if the subject meets dose escalation criteria (as defined below), after receiving at least 8 consecutive infusions at the initial dose. A further increase in dose to $3 \text{ mg}\cdot\text{kg}^{-1}$ qw may be considered if a subject continues to demonstrate persistence of disease manifestations after receiving at least 8 consecutive infusions at a dose of $3 \text{ mg}\cdot\text{kg}^{-1}$ qow.

Prior to considering a dose increase, the subject will be evaluated for other potential causes of any observed clinical manifestations (e.g., initiation of a potentially hepatotoxic concomitant medication in a subject with abnormal ALT or AST, missed study infusions, or development of viral or autoimmune hepatitis or other alternative etiology of liver disease or inadequate weight gain). Protocol defined clinical laboratory assessments will be modified around any dose modification, as described in [Section 5.9](#).

A subject **meets dose escalation criteria** when any of the following are present:

- ALT or AST remaining abnormal, and either not improved or worsened from Baseline after 8 consecutive infusions from Baseline or worsened from the previously achieved lowest value over the preceding 8 consecutive qow infusions;
- LDL-C or triglyceride remaining abnormal, and either not improved or worsened over the preceding 8 consecutive qow infusions;
- The subject is < 18 years of age at the time of assessment for dose escalation, has a WFA z-score that is 2 standard deviations below the mean that either did not improve or worsened during the preceding 6 months, and the subject did not miss more than 20% of study infusions during the preceding 6 months. All possible etiologies for inadequate weight gain, not related to LAL Deficiency, will be ruled out by the Investigator before considering a dose increase.

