⁸ Refer to [Section 5.9](#) for a list of analytes in each laboratory panel. Subjects ≥ 18 years of age must fast for at least 9 hours prior to collection of samples for the lipid panel and fasting serum glucose, and must abstain from alcohol for at least 24 hours prior to collection of blood for the liver and lipid panels. *Prior to any dose change, serum lipid, serum liver, hematology, chemistry, ferritin and hs-CRP shall be obtained; ADA and PK assessments will be obtained on the day of any study drug dose change, as described in [Section 5.9.4](#). Serum lipid and serum liver assessments should be taken 4, 8, and 12 weeks following any study drug or lipid drug dose change.*

⁹ A sample will be obtained at Screening, or as soon as practically possible thereafter ([Section 5.9.3](#))

¹⁰ For female subjects of childbearing potential only. Serum pregnancy test is required at screening. Urine pregnancy tests at all designated visits thereafter.

¹¹ PK Samples will be taken at Baseline, Week 24, Week 48, and on the first day of any dose modification as per [Table 2](#) and [Table 3](#).

¹² Vital signs will be measured at one time point during Screening. On the day of study drug dosing, vitals will be collected before dosing, every 30 minutes (±10 min) during the infusion, and every 30 minutes (±10 min) from 0 to 2 hours after infusion. Beginning at Week 24, the post-infusion period for vital sign monitoring may be shortened from

2 hours to 1 hour for subjects who have completed at least 22 weeks of treatment with no occurrence of moderate or severe IARs, contingent upon approval from the Sponsor.

- ¹³ Please refer to [Section 6.1](#) for details on treatment administration. Please refer to the IMP manual for detailed instructions on duration and rate of infusions. After Week 24, infusion time may be decreased to 1 hour. If the infusion is not well tolerated; the infusion rate may be decreased ([Section 6.5.2](#)). If dose is increased to weekly infusion, the allowable window for treatment is ± 2 days, and infusions must be at least 5 days apart.
- ¹⁴ Subjects should also be queried about any changes in lipid-lowering medications or lipid-lowering diets, UDCA, metformin, glitazones, or vitamin E.

Schedule I - Assessments for Adult Subjects (Subjects ≥18 years) - Week 52 to Week 96 of Treatment Period

| Assessments* | Treatment | | | | | | | | | | | |

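### Section 5.7 lets post-infusion vital-sign monitoring fall to 1 hour from Week 24 with no reset when the mg/kg dose is raised; returning to 2 hours for the first few infusions is a cheap precaution

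*Protocol*

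**What the plan says.** **Vital signs (protocol 5.7).** The standard is readings for 2 hours after the infusion. From Week 24 this may become 1 hour, with Sponsor approval, for "subjects who have completed at least 22 weeks of treatment with no occurrence of moderate or severe IARs". The stated way back is that "the post-infusion monitoring period may need to be extended back to 2 hours if subjects begin experiencing moderate or severe IARs". Extra readings are allowed at any time at the Investigator's discretion.

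**Infusion time (6.1).** The text reads "Up to and including Week 24, study infusions are recommended to be administered over approximately 2 hours" and then "After Week 24, infusions may be administered over approximately 1 hour, as tolerated by the subject". The Appendix B footnotes repeat both permissions and add: "If the infusion is not well tolerated; the infusion rate may be decreased". Section 6.5.2 and the footnotes refer to the IMP manual for duration and rate.

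**Dose steps (6.1.1, 6.1.2, synopsis).** The move from 1 to 3 mg/kg needs eight infusions in a row on the standard route and four on the accelerated route. No latest date is set, and the synopsis permits increases in both study periods.

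**What changes at a dose step.** Under 3.1 the visit plan "will be modified for subjects who have a dose change to allow for closer monitoring of laboratory values around the period of change". Section 5.9.4 adds laboratory panels and, for dose modifications, "at the first infusion of new dose/schedule, a predose blood sample will be collected for ADA and serial blood samples" for PK. Neither section mentions vital signs or infusion time.

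**The concern.** Both permissions are earned by time on treatment and absence of reactions, whatever the dose at which that record was built. A subject may earn them entirely at 1 mg/kg and carry them into the first infusions at 3 mg/kg.

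Safety is the primary objective and IARs are the event of special interest (2.1, 7.1.3). Section 1.4.1 reports that exposure rises more than in proportion to dose between 1 and 3 mg/kg. Section 7.1.3 says that most acute IARs to similar products arise within 2 hours of the infusion. A clean record at 1 mg/kg is therefore only partial support for a 1-hour watch at triple the dose.

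The protocol does tie one relaxation to dose. Home infusion under 6.5.2 requires an unchanged dose and regimen over the preceding 24 weeks. Sections 5.7 and 6.1 have no comparable condition. The SAP also treats a dose change as relevant to reactions: section 7.2.2.2 adds an IAR listing, showing prior dose, for subjects whose dose changed.

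**Working it through.** The plan states no figure on this point. The check uses nominal every-other-week visits (0, 2, 4, ...).

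**1. Can the step fall after Week 24?**
- Standard route: eight infusions at Weeks 0 to 14, so the earliest 3 mg/kg infusion is Week 16. Accelerated route: four infusions at Weeks 0 to 6, so Week 8. In special cases 6.1.2 allows less.
- Neither route has an upper limit.
- The pediatric growth criterion in 6.1.1 looks back over half a year and requires that "the subject did not miss more than 20% of study infusions during the preceding 6 months". Six months is about 26 weeks, so read literally it is not met before about Week 26, when both 1-hour permissions can already apply. The accelerated route can act sooner.

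**2. Does the rate cap prevent a 1-hour infusion of 3 mg/kg?**
- Inputs: cap 4 mL/kg/h (6.5.2); concentration 0.1 to 1.5 mg/mL (6.5.1).
- Lowest concentration that fits in 1 hour: 3 / 4 = 0.75 mg/mL, which is within range. At 1.5 mg/mL the volume is 3 / 1.5 = 2 mL/kg. The cap is no barrier.

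**3. What changes for the subject?**
- Planned observation from the start of infusion: 1 + 1 = 2 h, against 2 + 2 = 4 h.
- Hourly dose for a subject already on 1-hour infusions: from 1/1 = 1 to 3/1 = 3 mg/kg/h. Over 2 hours it would be 3/2 = 1.5 mg/kg/h.

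**4. What would a 4-infusion reset cost, for a step at Week w?**
- Infusions at the new dose already under 2-hour monitoring: (24 − w)/2, because 1-hour monitoring may begin at Week 24.
- Infusions at the new dose already given over 2 hours: (26 − w)/2, because the first 1-hour infusion is at Week 26.
- Extra hours for each part: max(0, 4 − count), with the count not below zero.

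| Step at week | Extra monitoring (h) | Extra infusion time (h) | Total (h) |
|---|---|---|---|
| 16 or earlier | 0 | 0 | 0 |
| 18 | 1 | 0 | 1 |
| 20 | 2 | 1 | 3 |
| 22 | 3 | 2 | 5 |
| 24 | 4 | 3 | 7 |
| 26 or later | 4 | 4 | 8 |

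Where PK sampling already keeps the subject on site for 2 hours after the first new-dose infusion (Tables 2 and 3), the maximum is about 8 − 1 = 7 h.

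The step from 3 mg/kg every other week to 3 mg/kg weekly is left out, because the dose per infusion does not change.

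**The case against.** The case on the other side is substantial.

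- **Control points exist.** Escalation and shortened monitoring both need Sponsor approval. Escalation also depends on acceptable tolerability of preceding infusions (3.1). Both 1-hour rules are permissive, and the Investigator may take more readings without waiting for a reaction. This stands, but none of these controls carries a dose criterion.
- **Reactions are managed.** Table 6 requires slowing or stopping the infusion, and dosing is suspended after a severe reaction until the Safety Committee has reviewed it. Infusions are supervised and emergency supplies must be at hand. Under 6.5.2 the first infusions after a step cannot be given at home. All this stands, though Table 6 and the suspension act only once a reaction has occurred.
- **The first new-dose infusion is partly covered.** PK samples run to 2 hours afterwards. That covers one infusion, does not require vital signs in the second hour, and for adults appears limited by 5.9.8 to severe liver disease or previous transplant.
- **Pharmacology and experience are reassuring.** Section 1.4.1 gives a half-life of 0.09 to 0.21 hours at 1 or 3 mg/kg, so 1 hour is about five half-lives or more (1/0.21 = 4.8). No subject in that study had an IAR, although its 3 mg/kg cohort had three subjects. Sections 1.5.1 and 1.5.2 describe 3 mg/kg as generally well tolerated. This weakens an exposure argument for the second hour without settling when reactions arise.
- **Four infusions is a choice.** In 6.1.2, four is an escalation interval that can be waived, not a tolerability run-in. This stands.

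A reader might infer that reactions would be missed. The documents do not support that: the IAR definition in 7.1.3 runs to 4 hours after the infusion and takes in later consistent symptoms, and adverse events are assessed continuously, whatever the vital-sign window.

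**Conclusion.** The point holds as a low-cost precaution. Section 5.7 has no condition on current dose and no reset at an increase in the mg/kg dose. The first 3 mg/kg infusions after a step past Week 24 may therefore be watched for 1 hour instead of 2.

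Two limits apply. First, only the monitoring half rests on the protocol alone. The infusion-time half, including the threefold hourly dose, assumes that the IMP manual sets no dose-specific duration; it was not available. Second, a reader might infer a known hazard, or a high reaction rate at 3 mg/kg. The documents show neither, and the reported experience points the other way.

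The cost figures assume nominal visits, a reset of four infusions, and a subject who would otherwise have used the 1-hour permissions. They apply to each mg/kg step. A reader might take 8 hours as a ceiling per subject, but 6.1.3 permits dose reductions, and a later re-escalation would repeat the cost.

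**What to change.** In 5.7 and the matching footnotes of Schedules I and II, state that after any increase in the mg/kg dose, post-infusion vital-sign monitoring returns to 2 hours for the first few infusions at the new dose: for example 4, or a number set by the Safety Committee. It may be shortened again only if these pass without a moderate or severe IAR. Four is a reasonable default because a Week 16 escalator already receives four 3 mg/kg infusions under 2-hour monitoring before Week 24.

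Check the IMP manual. If it does not already set the infusion time after a dose increase, add the same return to about 2 hours in 6.1 and the footnotes.

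The change needs a protocol amendment of a sentence or two. In subject time it costs up to 4 hours per mg/kg step for monitoring alone, or up to 8 hours if infusion time is also reset.

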5.8. Electrocardiogram

Age-appropriate 12-lead ECGs will be obtained at the time points specified in [Appendix B](#). ECGs will be reviewed by a qualified clinician, and any abnormalities will be specified as clinically significant (CS) or not clinically significant (NCS).

5.9. Clinical Laboratory Assessments

Blood and urine samples for clinical laboratory tests will be collected at the time points indicated in [Appendix B](#). [Table 1](#) lists the clinical laboratory tests to be performed in this study.

Note that not all tests are performed at the same time points. Due to the limitations on the volume of blood collection that is considered to be acceptable in young children with very small total circulating blood volumes, the laboratory tests will be ranked in the order corresponding to the study objectives, as follows:

5.9.1. Tier 1 Laboratory Assessments

Tier 1 assessments include safety laboratory tests, including serum chemistry (including glycosylated hemoglobin [HbA1c]), liver function tests, serum lipids, hematology, coagulation panel (local), serum human chorionic gonadotropin (hCG), ADA, DBS LAL enzyme activity, viral hepatitis screen, carbohydrate-deficient transferrin (CDT), and PK. These tests include all efficacy laboratory tests. If a subject's blood volume threshold for weight or clinical status limit collection of any Tier 1 laboratory assessments, the medical monitor should be consulted for guidance with regard to a modified schedule for that visit.

5.9.2. Tier 2 Laboratory Assessments

Tier 2 assessments include all other laboratory tests, including exploratory biomarkers, macrophage activation markers, and hsCRP. Tier 2 assessments are considered mandatory and all efforts will be made to collect these samples in all subjects as indicated in [Appendix B](#).

If a subject's blood volume threshold for weight or clinical status limit collection of samples on the scheduled visit date, the Tier 2 laboratory assessments may be collected at the next scheduled visit, or when clinical status permits.

Blood volume threshold based on subject weight is discussed further in the SOM.

The blood sample for deoxyribonucleic acid (DNA) extraction is not included in either tier of laboratory assessments, unless it is necessary to establish subject eligibility (e.g., for subjects with previous hematopoietic stem cell or liver transplant without evidence of LAL enzyme deficiency by DBS). For all other subjects, this sample may be collected whenever blood volume permits, preferably at Screening, or as soon as practically possible thereafter (see [Section 5.9.7](#)).

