4.3. Inclusion Criteria

A subject must meet all of the following inclusion criteria to be eligible for this study:

1. Subject will be > 8 months of age at the time of dosing.
2. Subject or subject's parent or legal guardian (if applicable) consents to participation in the study. If the subject is of minor age, he/she is willing to provide assent where required per local regulations, and if deemed able to do so.
3. Confirmation of LAL Deficiency diagnosis as determined by the central lab; a subject who received a liver or hematopoietic stem cell transplant who does not show evidence of LAL enzyme deficiency by dried blood spot (DBS) due to the effects of transplantation must have either:
 - a. Molecular genetic testing which confirms mutations in both alleles of the *LIPA* gene (*Note: in a highly suggestive case of LAL Deficiency where only 1 mutation is identified, subjects may be included based on a fibroblast enzyme activity assay*); **OR**
 - b. Appropriately documented (based on consultation with the Sponsor) historical result of an enzyme test prior to hematopoietic or liver transplantation (performed in DBS, leukocytes or fibroblasts).
4. Subjects > 8 months but < 4 years of age at Screening will have at least 1 of the following documented clinical manifestations of LAL Deficiency:
 - a. Dyslipidemia (defined as Screening LDL-C > 130 mg/dL; TG > 200 mg/dL);
 - b. Elevated transaminases (ALT ≥ 1.5 x ULN (based on the age- and gender-specific normal ranges of the central laboratory performing the assay);

- c. Impaired growth as defined as:
 - i. WFA or SFA less than the age- and gender- appropriate 5th percentile on a standard WHO (subjects \leq 24 months of age) or CDC (subjects $>$ 24 months and $<$ 4 years of age) WFA or SFA chart for at least 3 months prior to study entry; **OR**
 - ii. Poor weight gain as evidenced by calculated weight percentile decreasing across 2 major percentile (99th, 97th, 95th, 90th, 75th, 50th, 25th, 10th, 5th, 3rd, and 1st) lines on a standard WHO (subjects \leq 24 months of age) or CDC (subjects $>$ 24 months and $<$ 4 years of age) WFA chart over a period of 6 months prior to study entry;
 - d. Suspected malabsorption with:
 - i. Persistent unexplained gastrointestinal symptoms such as nausea, diarrhea, abdominal pain, and bloating; **OR**
 - ii. Unexplained anemia, or other abnormalities suggestive of malabsorption (e.g., osteomalacia, hypoalbuminaemia, prolonged bleeding time due to vitamin K deficiency); **AND**

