5.9.6. LAL Enzyme Activity in Dried Blood Spots

A blood sample will be spotted on filter paper at the site for each subject and then shipped to the central laboratory for measurement of DBS LAL enzyme activity. A sample will be collected from all subjects, irrespective of whether historical LAL activity data are available. For subjects who have undergone liver transplantation the DBS will be performed, but it will not be used to determine study eligibility. Samples will be collected at the time points specified in [Appendix B](#).

All samples will be assayed by a central laboratory to ensure consistency of LAL activity measurements across all subjects in the study. Refer to the SOM and Laboratory Manual for further details regarding the collection, processing, and storage of this sample.

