5.9.7. DNA Sample

The Sponsor intends to analyze pharmacogenetics in the sebelipase alfa program in order to explore how genetic variations may affect clinical parameters associated with sebelipase alfa use and LAL biology. DNA sequences, including both the protein coding sequence and sequences that regulate gene transcription, messenger ribonucleic acid stability and the efficiency of protein translation that may be investigated include:

1. LAL (LIPA);

Genes coding for other proteins involved in lipid biology that may contribute to and/or modify the disease phenotype of LAL Deficiency (e.g. ABCA1);

2. Genes that may modify susceptibility to AEs related to sebelipase alfa.

Where local regulations permit and subject to discretionary approval from each center's IRB/IEC, a blood sample for DNA extraction will be collected from each subject at Screening, or as soon as practically possible thereafter, for subjects who do not require sample collection to establish study eligibility. The DNA will be used as part of a later pooled analysis, which will include a determination of the spectrum of LAL mutations in subjects with LAL Deficiency and the relationship between gene mutation, safety, efficacy, and susceptibility to development of ADAs. The Sponsor will only analyze DNA sequences within genes relevant to the mode of action and response to sebelipase alfa, including variants important in understanding AEs, and candidate genes with a potential role in the etiology, pathogenesis, and progression of LAL Deficiency. No additional testing will be performed on the samples collected in the study.

DNA samples will be stored by the Sponsor, or designee, in a secure, monitored, and controlled environment until analysis, and will be destroyed by the Sponsor after all worldwide obligations have been met, or sooner if required by local regulations.

Refer to the SOM and Laboratory Manual for further details regarding the collection, processing, and storage of these samples.

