7.1.3.4. Baseline LAL Enzyme Activity and DNA Results

The number and percentage of subjects with LIPA gene sequencing results consistent with LAL-D and with fibroblast results consistent with LAL-D will be presented. In addition, the number and percentage of subjects homozygous for common mutation, heterozygous for common mutation, with another mutation, or no variants found will be presented. LAL Enzyme Activity at baseline will be categorized as affected (<=0.016 nmol/punch/hr), carrier (0.017 to 0.026 nmol/punch/hr); and unaffected (0.027 to 0.0152 nmol/punch/hr) are summarized.

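### After a stem cell transplant, blood DNA and dried-blood-spot enzyme activity can be the donor's, but the protocol names only blood as the DNA sample and the SAP has no rule for such results.

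*Protocol*

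**What the plan says.** Criterion 3 (Protocol 4.3) accepts that a transplant can hide the enzyme defect in a dried blood spot (DBS). A recipient "who does not show evidence of LAL enzyme deficiency by dried blood spot (DBS) due to the effects of transplantation must have either" a genetic result (3a) or a documented pre-transplant enzyme test (3b). Route 3a reads "Molecular genetic testing which confirms mutations in both alleles of the" LIPA gene and does not state a specimen. A note to 3a covers highly suggestive cases with only one mutation found: "subjects may be included based on a fibroblast enzyme activity assay".

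The specimen appears elsewhere. Section 5.9.2 gives the blood sample for DNA priority where judged "necessary to establish subject eligibility (e.g., for subjects with previous hematopoietic stem cell or liver transplant without evidence of LAL enzyme deficiency by DBS"), taking stem cell and liver recipients together. Section 5.9.7 says that "a blood sample for DNA extraction will be collected from each subject at Screening" or soon after, and names no other tissue. On the DBS, section 5.9.6 makes an exception for one group only: "For subjects who have undergone liver transplantation the DBS will be performed, but it will not be used to determine study eligibility".

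In the SAP, 7.1.3.4 states that "the number and percentage of subjects homozygous for common mutation, heterozygous for common mutation, with another mutation, or no variants found will be presented". Section 7.12 uses three of those four categories as an efficacy subgroup factor; it has none for subjects with no variants found. Section 7.9 classifies enzyme activity from the DBS, or from whole blood if there is no DBS, and tabulates shifts from baseline. None of the three sections mentions transplantation.

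**The concern.** A stem cell transplant replaces the cells that both tests read. If the DBS looks normal because the blood is the donor's, DNA from that blood is the donor's too, so the fallback test fails for the same reason as the first. Liver recipients keep their own blood cells, yet 5.9.2 treats the two groups alike.

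Two things are at stake. One is eligibility: prior stem cell recipients are a named target population (Protocol 4.1), and a true case could be turned away. The other is the tables: the SAP would report a donor's genotype or enzyme category as the subject's own, and a wrong mutation label would look no different from a right one.

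**Working it through.** The plan gives no figure to reproduce here. The check is a cross-reading plus a short enumeration.

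**Inputs from the documents**
- Blood is the only DNA sample collected (Protocol 5.9.2, 5.9.7). Two mutated alleles are required (criterion 3a).
- Transplants less than 2 years before dosing are excluded (Protocol 4.4, criterion 4).
- Appendix B, footnote 1: historical DNA is assessed in transplant recipients when no enzyme deficiency was documented before transplant. It does not say that the DNA must predate the transplant.
- A subgroup summary needs at least 5 subjects in each subgroup (SAP 7.12).
- Expected number treated: about 30 (Protocol 8.2), or not more than 20 (SAP 9.3).

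**Assumptions not in the documents**
- Blood cells are fully donor-derived after engraftment.
- For the probabilities, the donor is an unaffected full sibling and each parent carries one mutated allele.

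**Step 1: eligibility.** An unaffected donor has at most one mutated allele, so fully donor-derived blood cannot meet 3a. The remaining routes are 3b, DNA that predates the transplant, and the fibroblast note. On post-transplant blood that note opens only if exactly one mutation is seen, that is, if the donor is a carrier.

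**Step 2: donor genotype.** Of the four equally likely sibling genotypes, three are unaffected. Two of these are carriers and one has no mutation:
- P(carrier | unaffected) = (2/4)/(3/4) = 2/3
- P(no mutation | unaffected) = (1/4)/(3/4) = 1/3

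In the SAP's categories:

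| Patient's own genotype | Reads heterozygous common | Reads other | Reads no variants | Wrong 7.12 subgroup | No 7.12 category |
|---|---|---|---|---|---|
| common/common | 2/3 | 0 | 1/3 | 2/3 | 1/3 |
| common/other | 1/3 | 1/3 | 1/3 | 1/3 | 1/3 |
| other/other | 0 | 2/3 | 1/3 | 0 | 1/3 |

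A carrier donor can therefore put the subject in the wrong subgroup. A non-carrier donor puts the subject under 'no variants found' in 7.1.3.4 and in no 7.12 category.

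**Step 3: enzyme activity.** SAP 7.9 takes improvement over subjects affected or carrier at baseline, and worsening over subjects unaffected or carrier at baseline. Compare a subject who would be affected on their own blood:

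| Baseline category | In improvement denominator | In worsening denominator |
|---|---|---|
| affected (own blood) | yes | no |
| carrier (donor-type) | yes | yes |
| unaffected (donor-type) | no | yes |

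The baseline category and the shift denominators change. Enzyme activity is not a 7.12 factor, so the subgroups do not. Separately, the unaffected range is printed as 0.027 to 0.0152, whose upper end lies below its lower end; a normal value cannot be placed until that is corrected.

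**Step 4: size.** The number of stem cell recipients is not given. One subject is 1/5 = 20% of a minimum-size subgroup, 1/20 = 5% of 20 subjects and 1/30 = 3.3% of 30. Three subjects, taken only as an illustration, are 3/20 = 15% or 3/30 = 10%. With none, the effect is nil.

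**The case against.** A reader might infer that the diagnosis cannot be confirmed in stem cell recipients. The documents do not support that. Route 3b accepts a pre-transplant enzyme test, 3a does not itself require current blood, and Appendix B collects historical DNA. Exclusion follows only if 3b and pre-transplant DNA are both missing and the fibroblast note does not apply. Under the sibling assumption a carrier donor, with probability 2/3, would supply the single mutation that opens that note.

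A reader might also infer that leaving stem cell recipients out of the 5.9.6 exception excludes them. It does not, because criterion 3 already lets a recipient with a non-deficient DBS go on to 3a or 3b. A blanket exception would also discard useful evidence: a deficient DBS after a stem cell transplant is informative, since a healthy donor's blood would not produce it.

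Other points against also carry weight. Section 5.9.2 is about blood-volume priority. The SAP does not name the DNA specimen, and 7.1.3.4 also tabulates fibroblast results. Mixed donor and recipient blood would soften the effect. All data are listed by subject, and no formal testing is planned.

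What remains is that the only DNA sample the protocol collects is blood, historical DNA is not required to predate the transplant, and the SAP has no rule to keep donor results out of three sets of tables.

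**Conclusion.** The gap is real but minor. On fully donor-derived blood, criterion 3a cannot be met, and the likely error is the wrongful exclusion of a true case that lacks pre-transplant evidence. In the SAP, a carrier-donor genotype can enter the wrong mutation subgroup, a non-carrier result drops out of 7.12, and a donor-type baseline DBS distorts the enzyme category and shift tables.

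The direction rests on general knowledge that blood is donor-derived after engraftment. The 2/3 and 1/3 rest on an unaffected full-sibling donor with carrier parents; the documents give no basis for figures with other donors. The documents also do not support a definite share of the tables, or a claim that such subjects decide whether a mutation category reaches 5, because the number of stem cell recipients may be zero. No primary conclusion depends on this: the primary objective is safety and the affected summaries are descriptive.

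**What to change.** - **Protocol 5.9.2, 5.9.7 and criterion 3a:** state that for prior stem cell recipients the LIPA genotype comes from a pre-transplant DNA result or from non-blood material, such as the fibroblasts already named in 3a, and not from post-transplant blood. Say in Appendix B, footnote 1, that historical DNA from these subjects must predate the transplant.
- **Protocol 5.9.6:** state that a non-deficient DBS after stem cell transplant does not count against eligibility, while a deficient one may still be used.
- **SAP 7.1.3.4, 7.9 and 7.12:** classify these subjects by the pre-transplant or fibroblast result, otherwise as not assessable. Leave their post-transplant DBS and whole-blood results out of the category and shift tables, and list them with a flag.

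The cost is a short protocol clarification and a few lines of SAP text. Where no pre-transplant result exists, non-blood material may have to be obtained. A few subjects may appear as not assessable.
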